#### **Number of Patients (planned):**

~180

#### **Diagnosis and Criteria for Inclusion:**

### **Subject Inclusion Criteria:**

Patients must meet all of the following inclusion criteria to be eligible for enrollment into the study:

- 1. Provide signed informed consent which includes pharmacogenomic (PGx) testing.
- 2. Have a diagnosis of MDD without psychotic features, according to the *Diagnostic and Statistical Manual of Mental Disorders*, 5th Edition (DSM-5) criteria, based on clinical assessment and confirmed by the Mini International Neuropsychiatric Interview (MINI).
- 3. TRD documented in the Massachusetts General Hospital (MGH) Antidepressant Treatment Response Questionnaire (ATRQ) (5-year version). That is:
  - a. clinically meaningful inadequate response (estimated < 50% improvement per investigator/patient consensus and documented by the investigator) with:
    - 1) at least 2 treatment courses with antidepressant regimens;
    - 2) used at least 2 different pharmacologic treatment classes (eg, SSRI, SNRI, TCA, MAOI, atypical); or if only one class treatment is used, at least one combination treatment course;
    - 3) the doses have been given at accepted therapeutic doses for an adequate duration (at least 6 weeks), per product label;
    - 4) One of these inadequate response must occur within the current episode.

**Note**: non-pharmacological treatment (eg, cognitive behavioral therapy, electroconvulsive therapy, repetitive transcranial magnetic stimulation, vagus nerve stimulation, acupuncture) are not counted as treatment regimen.

4. To be eligible, patients must have DGM4 genotype results obtained from the designated Clinical Laboratory Improvement Amendments (CLIA) lab, and all eligible DGM4-positive

patients and about 20% DGM4-negative patients will be randomly included by an IRT system in order to achieve the appropriate randomization ratio of DGM4-positive vs negative patients.

- 5. Pregnancy conception limitations
  - Female patients must be postmenopausal or surgically sterile or, if of childbearing potential and the partner is not vasectomized (6 months minimum), must agree to use a medically acceptable form of contraception from the time of signing the informed consent form (ICF) through at least 60 days following the last administration of study drug. If only the barrier method is used, a double barrier must be employed. Postmenopausal women must have had ≥ 24 months of spontaneous amenorrhea. Surgically sterile women are defined as those who have had a hysterectomy, bilateral ovariectomy, or bilateral tubal ligation. All women of childbearing potential must have a negative pregnancy test result before administration of study drug.
  - Male patients must be biologically incapable of having children (eg, vasectomized) or
    must agree to use the above forms of birth control for themselves and their partner from
    the time of signing the ICF through at least 120 days following the last administration of
    study drug.
- 6. Be fluent in the local language.
- 7. Male or female aged 18 to 70, inclusive, at time of Visit 1.
- 8. Have a HAMD-17 total score  $\geq$  21 at screening and baseline.
- 9. Be willing to discontinue the use of antidepressant drugs (including over-the-counter medications to treat depression [eg, St John's Wort]) at least 5 half-lives (or at least 1 week for herbal or other over-the-counter medications for depression) prior to baseline (Day -1). For fluoxetine, a washout period of at least 3 weeks for ≤ 20 mg/day and at least 4 weeks for > 20 mg/day is required.

#### **Subject Exclusion Criteria:**

Patients with any of the following characteristics/conditions will be excluded from the study:

- 1. Prior participation in a study with liafensine.
- 2. Used any investigational drug product, device, or biologic within 3 months or 5 half-lives (whichever is longer) prior to baseline (Day -1).
- 3. A positive pregnancy test result or currently breastfeeding.
- 4. Clinically significant and/or unstable illness (including chronic, persistent, or acute infection), medical/surgical procedure, or trauma within 30 days prior to screening or between screening and baseline (Day -1) as determined by the investigator.
- 5. A history or presence of a clinically significant and/or unstable hepatic, renal, gastrointestinal, cardiovascular, endocrine, respiratory, immunologic, hematologic, dermatologic, or neurologic abnormality, or any other condition, that in the investigator's opinion, represents potential risk to the patient's safety and ability to fully participate in the study, or affects the absorption, distribution, metabolism, or excretion of liafensine.
- 6. Presence of autoimmune hepatitis, primary sclerosing cholangitis, untreated hepatitis C, active hepatitis B, or any other uncontrolled or unstable liver disease according to local guidance.
- 7. Uncontrolled human immunodeficiency virus (HIV) infection according to local guidance.
- 8. Uncontrolled abnormal thyroid function according to local guidance.

- 9. One or more clinical laboratory evaluations are outside the reference range, at screening, that are in the investigator's opinion, of potential risk to the patient's safety.
- 10. Has at the Screening Visit:
  - Alanine aminotransferase (ALT) or aspartate aminotransferase (AST) levels > 1.5x the upper limit of normal (ULN) at screening.
  - Total bilirubin (TBL) > 2 mg/dL (34.2 μmol/L) at screening, unless there is an explained indirect hyperbilirubinemia, eg, Gilbert's syndrome.
  - Alkaline phosphatase (ALP) > 1.5x the ULN at screening.

**Note**: Laboratory tests can be repeated to see if values return to normal range, but any such laboratory abnormality must be resolved by the Baseline Visit (Day -1).

- 11. Clinically significant vital sign abnormality at screening. This includes, but is not limited to, the following, in the supine (after at least 5 min rest) and standing (after 1 min and 3 min standing): systolic blood pressure ≥ 140 mmHg; diastolic blood pressure ≥ 90 mmHg; or heart rate < 50 or > 90 beats per minute. If the initial blood pressure is ≥ 140/90 mmHg, the lowest value from up to 3 additional attempts, which also must not be ≥ 140/90 mmHg, should be used. Patients with symptomatic orthostatic hypotension, at the discretion of investigator, will be excluded.
- 12. Corrected QT interval measurement according to the Fridericia rule (QTcF) > 450 msec for men and > 470 msec for women during controlled rest at screening, or history of long-QT syndrome.
- 13. ECGs containing any of the following readings:
  - Left bundle branch block
  - Right bundle branch block with QRS duration > 140 ms
  - Intraventricular conduction defect with QRS duration > 140 ms
  - Long QT syndrome
- 14. History of seizure, other than childhood febrile seizures.
- 15. History of clinically significant head trauma, including closed head injury with loss of consciousness, that is, in the opinion of the investigator, likely to affect central nervous system function.
- 16. History of clinically significant symptomatic orthostatic hypotension (ie, postural syncope).
- 17. History of narrow angle glaucoma.
- 18. History of cancer within 2 years prior to screening or between screening and baseline (Day -1), except for non-metastatic basal and/or squamous cell carcinoma of the skin.
- 19. Use of prescription or nonprescription medications for attention-deficit hyperactivity disorder (ADHD), narcolepsy, or cognitive enhancement (eg, methylphenidate, atomoxetine, modafinil, ginkgo biloba, and huperzine A) within 30 days prior to screening or between screening and baseline (Day -1).

- 20. Regular consumption of (eg, more days than not) excessive quantities of xanthine-containing beverages (eg, more than five cups of coffee or the equivalent per day) within 30 days prior to screening or between screening and baseline (Day -1).
- 21. Urine drug screen (UDS) positive for a drug of abuse, with the exception of cannabis in countries where it is legally available (see Table 3 for list of drugs of abuse). Where legal, prior use of cannabis is permitted provided the patient agrees to abstain from smoking or ingesting cannabis or cannabis products during the study.
- 22. Use of potent inducers of CYP3A4 (eg, rifampin, rifabutin, phenytoin, carbamazepine, or phenobarbital) within 2 weeks prior to baseline (Day-1).
- 23. Current diagnosis or history of a psychotic disorder, MDD with psychotic features, manic or hypomanic episode of bipolar or related disorders.
- 24. Current diagnosis of anxiety disorder (if primary), post-traumatic stress disorder, obsessive-compulsive disorder (if primary), intellectual disability (DSM-5 diagnostic code 319), borderline personality disorder, antisocial personality disorder, histrionic personality disorder, or narcissistic personality disorder according to the DSM-5 criteria, or any other psychiatric or neurologic disorder or symptom due to a general medical condition, that, in the judgement of the investigator, could pose undue risk to the patient or compromise the study.
- 25. Hospitalized or discharged from psychiatric ward within 8 weeks prior to the screening visit and planned hospitalization for any condition(s) during the study.
- 26. Moderate or severe alcohol use disorder or other substance use disorder (except nicotine or caffeine), within 6 months prior to screening, according to the DSM-5 criteria.
- 27. Significant risk of suicide determined by:
  - a. Acute suicidality as evidenced by answering "yes" to Question 5 ("In the Past Year") on the C-SSRS, indicating active suicidal ideation with specific plan and intent for suicide, at screening, or baseline (Day -1); or
  - b. History of suicidal behavior as indicated by a "yes" response on the Suicidal Behavior section of the C-SSRS ("In the past year") or
  - c. A score ≥ 5 on Item 10 (suicidal thoughts) of the MADRS at screening or baseline (Day -1); or
  - d. Has attempted suicide within 6 months prior to the initial screening visit.
- 28. Previous allogenic bone marrow transplant.
- 29. Received non-leukocyte-depleted whole blood transfusion within 4 months prior to PGx testing at Screening.
- 30. Currently employed by the sponsor or by a clinical trial site participating in this study, or a first-degree relative of an employee of the sponsor or of an employee at a participating clinical trial site.

#### **Concomitant Treatment and Study Restrictions:**

**Prohibited** concomitant treatments and study restrictions during the study from baseline to 14 days after the last dose of study drug (the first half of the follow-up) include:

- 1. Any investigational drug product, device, or biologic.
- 2. Any prescription or nonprescription medication for ADHD, narcolepsy, or cognitive enhancement (eg, methylphenidate, atomoxetine, modafinil, ginkgo biloba, and huperzine A).
- 3. Any psychopharmacologic drug (including antidepressants and over-the-counter medications to treat depression (eg, herbal medicines like St John's Wort, or other local herbal medicines).
- 4. Potent inducers of CYP3A4 (eg, rifampin, rifabutin, phenytoin, carbamazepine, or phenobarbital).

**Permitted** concomitant treatments, provided they meet the specific requirements detailed below, during the study and during the indicated periods include:

- 1. Up to 3 g/day paracetamol/acetaminophen.
- 2. Non-psychopharmacologic drugs provided the dose and condition being treated have been relatively stable for at least 2 months prior to screening and between screening and baseline (Day -1) and are not expected to change meaningfully during the study.
- 3. Soporific drugs may be used provided the dose and condition being treated have been relatively stable for at least 2 months prior to screening and between screening and baseline (Day -1) and are not expected to change meaningfully during the study.
- 4. Psychotherapy (including cognitive behavioral therapy) is permitted provided psychotherapy was initiated at least 2 months prior to screening and is expected to remain relatively stable during the study.
- 5. Anxiolytic drugs which do not affect 5-HT, norepinephrine, and dopamine activity may be used provided the dose and condition being treated have been relatively stable for at least 2 months prior to screening and between screening and baseline (Day -1) and are not expected to change meaningfully during the study.

**Note 1:** if a pro re nata (PRN) use has been established prior to the study, and not expected to change during the trial, this is considered stable treatment.

**Note 2**: Medication considered necessary for the patient's safety and well-being may be given at the discretion of the investigator and recorded in the appropriate sections of the electronic Case Report Form (eCRF). If a psychopharmacologic medication that is otherwise prohibited is administered the study measurements such as MADRS and CGI should be collected prior to dosing when possible. If any medication that is otherwise prohibited is administered to a patient, the investigator should inform the medical monitor prior to administration of medication when possible.

#### Other restrictions include:

- 1. Patients will be required to maintain their normal intake of xanthine-containing foods or beverages, and, if permitted, vitamin and herbal supplements, during the study, including the screening and follow-up periods.
- 2. Patients should not provide blood or plasma donations between screening and baseline (Day -1), during the study and for 6 weeks after the last dose of study drug.

### Investigational Product, Dosage, and Mode of Administration:

Investigational product (study drug) will be supplied as tablets containing 1 mg liafensine or matching placebo. Study drug will be taken orally, once daily in the morning (AM). Patients will be instructed to take the study drug whole, and not to chew, divide, or crush the tablets.

#### Randomization Phase:

Liafensine 1 mg QD

• Day 1 through Day 42: one 1 mg liafensine tablet and one matching placebo tablet QD

Liafensine 2 mg QD

- Day 1 through Day 7: one 1 mg liafensine tablet and one matching placebo tablet QD
- Day 8 through Day 42: two 1 mg liafensine tablets QD

Placebo QD

• Day 1 through Day 42: two placebo tablets QD

Further details regarding the packaging, storage, handling, and administration of study drug will be provided in the study Pharmacy Manual.

#### **Duration of Study Participation:**

The duration of participation for individual patients will be up to 91 days or longer, including an up to 21-day screening period (screening period may exceed 21 days if a prolonged washout of prior drug is required), a 6-week double-blind treatment period, and 2 post-study follow-up visits (at 14 days and 28 days after the last dose of study drug).

### Reference Therapy, Dosage and Mode of Administration:

None.

#### **Criteria for Evaluation:**

#### Efficacy:

The primary efficacy outcome measure is the change in MADRS total score from baseline (Visit 3, Day -1) to Visit 7 (Day 42) in DGM4-positive patients.

Other assessments include CGI-S, CGI-I and SDS. See Table 1 for the overall schedule of efficacy assessments. Note that CGIs should be completed only after the Patient Rated Depression and Functioning Checklist (PRDF Checklist) has been completed as instructed.

# Pharmacokinetics:

Blood samples will be collected for determination of concentrations of liafensine and its primary metabolite on Day 28 (Visit 6) and on Day 42 (Visit 7) prior to dosing. The time of prior dose and time of blood collection will be recorded.

If the patient discontinues before Day 42 (Visit 7), a blood sample will be collected for PK on the last day the patient takes a full dose of study drug or as soon as possible thereafter, but within 3 days after the last dose in any case. When possible, and if medically appropriate, blood samples should be collected for PK from patients who experience a serious adverse event (SAE) or overdose.

#### Pharmacogenomics:

PGx testing is required to determine eligibility for the study. PGx analysis may determine the association between genetic variations and the patient's response to treatment with liafensine.

#### Safety:

Safety will be assessed based on spontaneously reported AEs; the DESS scale; physical, neurological, and psychiatric examinations (including C-SSRS); vital signs including orthostatic changes in blood pressure and heart rate; weight; 12-lead ECGs; clinical laboratory test results; serum and urine pregnancy tests (females of childbearing potential only); and concomitant medication assessments. Safety assessments in addition to those specified may be performed to ensure patient safety if judged appropriate by the investigator.

See Table 1 for the overall schedule of safety assessments.

Psychiatric assessments will be performed by a psychiatrist or trained and certified clinical staff member. Neurologic assessments will be performed by an experienced clinician.

Patients fulfilling Hy's law, defined as [ALT or AST  $\geq$  3 × ULN] and [TBL  $\geq$  2 × ULN], in the absence of significant increase in ALP and in the absence of an alternative diagnosis that explains the increase in total bilirubin, will be discontinued, with medical follow-up as appropriate.

An IDMC will be established to monitor data on an ongoing basis to ensure the continuing safety of patients enrolled in this study. The IDMC will comprise individuals external to the sponsor and will consist of at least one medical expert in the relevant therapeutic area, at least one hepatologist, and at least one statistician. The IDMC's responsibilities, authorities, and procedures, with details of decision-making guidance and dissemination of the results, will be documented in the IDMC charter.

#### **Statistical Methods**:

#### Efficacy Analyses:

Efficacy analyses will be performed on the Full Analysis Set (FAS), which includes all randomized patients who took at least one dose of study drug and had a post-randomization efficacy evaluation. The FAS population will be analyzed by treatment randomized regardless of the actual treatment received.

The primary and secondary efficacy results of the study will be based on analysis in FAS patients with DGM4-positive biomarker.

The primary efficacy endpoint is the change in MADRS total score from baseline (Visit 3, Day -1) to Day 42 (Visit 7), in DGM4-positive patients. The primary efficacy analysis will be performed at 2-sided significance level of 0.05 using a mixed model for repeated measures (MMRM) that includes the fixed effects of treatment, visit (categorical covariate), treatment-by-visit interaction, baseline MADRS total score (continuous covariate), and region. An unstructured variance-covariance matrix will be used. The least-squares (LS) mean change in MADRS total score at Day 42 from baseline for the combined liafensine treatment arms (1 mg QD and 2 mg QD) and placebo arm will be estimated from the MMRM model. Prior work suggests that both doses of liafensine may be efficacious, therefore, the treatment effect for the combined liafensine treatment arms vs placebo will be estimated using the LS means' difference at Day 42 from the MMRM model. The comparison of the change in MADRS total score from baseline to Day 42 between each of the 2 liafensine treatment arms and placebo will be carried out using the same approach.

The key secondary efficacy endpoint will be the change from baseline in CGI-S at Day 42 in DGM4-positive patients. CGI-S will be analyzed using the same MMRM model as for the primary efficacy endpoint.

Other secondary efficacy endpoints include CGI-I and SDS at Day 42 as continuous endpoints. These endpoints will be analyzed using the same MMRM model as for the primary efficacy endpoint.

The exploratory efficacy results of the study will also be based on analysis in FAS patients.

Response rate, remission rate, and corresponding 95% confidence interval (CI) for each treatment

group will be derived by using Clopper-Pearson method. The comparison of response rates and remission rates between treatment groups at Day 42 will be carried out using the Cochran–Mantel–Haenszel (CMH) test.

Subscales, individual items, and domains of endpoints will also be analyzed in an exploratory manner, using the same MMRM model as for the primary efficacy endpoint.

The change in MADRS total score from baseline in DGM4-negative patients will be analyzed using the same approach as described for the primary endpoint analysis in the DGM4-positive patients. The LS mean of the change in MADRS total score for each treatment group and the treatment difference in DGM4-negative patients will be estimated. The treatment effects between the DGM4-positive and negative patients will be compared primarily in descriptive fashion to examine the trend, and may be evaluated by including the interaction of DGM4 status and treatment group in the mixed model.

### Safety Analyses:

Safety analyses will be conducted in the safety population, which includes all randomized patients who have received at least one dose of study drug. The safety population will be analyzed by the actual treatment received regardless of treatment randomized.

The incidence and severity of treatment-emergent adverse events (TEAEs) will be summarized by treatment. Vital signs including orthostatic changes in blood pressure and heart rate, weight, ECG, clinical laboratory evaluation, DESS scale, and C-SSRS data will be summarized with descriptive statistics, by visit and by treatment.

Safety and tolerability data will be summarized descriptively, including tables, listings, and graphs, as appropriate. Unless otherwise stated, descriptive summary statistics for continuous variables will include number (N), mean (ie, arithmetic mean), standard deviation (SD), minimum, median, and maximum. Descriptive summary statistics for categorical data will include frequency and proportion.

All data will be presented by treatment regimen.

Individual data for vital signs including supine and standing blood pressure and heart rate, weight, clinical laboratory measures, and ECG assessments will be listed and summarized for any potentially clinically important (PCI) values according to predetermined PCI criteria.

There will be no imputation (substitution) for missing data unless explicitly specified otherwise in this protocol or in the statistical analysis plan.

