# 2.1.3. Safety Objectives

- To compare the safety and tolerability of liafensine vs placebo in all randomized patients with TRD who received at least one dose of study drug during double-blind treatment
- To evaluate safety for liafensine 1 mg QD and 2 mg QD vs placebo in both DGM4-positive and DGM4-negative patients

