3.8.6. Discontinuation-Emergent Signs and Symptoms Scale

Discontinuation-Emergent Signs and Symptoms Scale (DESS) is used to monitor patients for discontinuation symptoms (Rosenbaum 1998). It includes 43 signs or symptoms for which the patient indicates whether there has been any change since their last visit – indicating new symptom, old symptom but worse, old symptom but improved, old symptom but unchanged, symptom not present. The DESS total score on a given day is calculated as the count of items with new symptoms or old symptoms but worse over all 43 items. For missing items, it will be imputed as the average from the non-missing items. The total score can range from 0 to 43. The number and proportion of subjects with the sum of zero, 1, 2, 3, and ≥ 4 will be presented each day and by the treatment arm. Treatment comparison will be performed each day from Day 1 to Day 14 using the Cochran-Mantel-Haenszel (CMH) test stratified by region and biomarker status. The average DESS total score over the assessment period will be calculated for each subject and compared between treatment group using the Wilcoxon rank-sum test.

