5.5. Safety Analysis

5.5.1. Adverse Events

Adverse events will be coded using MedDRA Version 25.0 or higher.

A TEAE is any AE that starts on or after the first day of study treatment or that worsens on or after the first day of study treatment, and within 30 days of the last administration of study treatment.

For the purpose of regulatory reporting, relationships of "Related" or "Unrelated" will be assessed and presented. Related to study drug suggests there is as at least a reasonable possibility that the drug caused the AE (ie, there is evidence or arguments to suggest a causal relationship between the drug and AE).

Unrelated to study drug will be assessed based on the following:

- Does not follow a reasonable temporal sequence from administration of drug
- Does not appear to worsen when the drug is re-administered
- There is not a reasonable possibility that the drug caused the AE
- An alternate etiology has been established, ie, the AE is more likely explained by another cause (eg, other study treatments or procedures, underlying medical conditions, concomitant medications, etc) than the study treatment

Missing relationships will not be imputed.

Potential liver injury, ie, suspected and/or confirmed Hy's Law, and drug-induced liver injury (DILI) cases will be assessed as adverse events of special interest (AESIs) and must be reported as serious adverse events. Information of abnormal laboratory test results including the course and evolvement, clinical signs and symptoms, detailed medical history and concurrent medication, history and current lifestyle including alcoholic assumption, and history of exposure to environmental chemical agents will be used to assess the case(s).

An overall summary of TEAEs using frequencies and percentages of subjects will be presented based on the following categories:

- TEAEs
- Study drug related TEAE
- TEAE by worst severity
- Serious TEAE
- Study drug related serious TEAE
- TEAEs leading to study drug withdrawal
- TEAEs leading to study drug being on hold
- TEAEs leading to death
- AESIs

The following events will be tabulated by SOC and PT. SOC will be sorted by descending frequency and then alphabetically for tie. Within each SOC, PT will also be sorted by descending frequency and then alphabetically for ties, by the overall number of subjects. If a SOC or PT is reported more than once for a subject, the subject will only be counted once in the incidence for that SOC or PT.

- TEAEs

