5.5.2. Clinical Laboratory Evaluation

Blood chemistry, hematology, and urinalysis tests are listed in Table 3.

Table 3. Clinical Laboratory Tests

Blood Chemistry	Hematology	Urinalysis
 Alanine aminotransferase (ALT/SGPT) Alkaline phosphatase (ALP) Aspartate aminotransferase (AST/SGOT) Bilirubin (direct and total) Blood urea nitrogen (BUN) Calcium Chloride Cholesterol (total) Creatine kinase (CK) Creatinine Glucose (serum) Phosphorus Potassium Protein (albumin and total) Sodium 	 Hematocrit Hemoglobin MCH concentration (MCHC) Mean corpuscular hemoglobin (MCH) Mean corpuscular volume (MCV) Platelet count Red blood cell (RBC) count White blood cell (WBC) differential Neutrophil count (absolute and %) Lymphocyte count (absolute and %) Monocyte count (absolute and %) Eosinophil count (absolute and %) Basophil count (absolute and %) WBC count 	 On-site macroscopic examination Central lab microscopic examination (in the event of protein, blood, nitrite and/or leukocyte esterase noted in macroscopic) Bilirubin Blood (occult and cells) Ketones Leukocytes Nitrite pH Protein Specific gravity Urobilinogen

Actual value, change from baseline, and percentage change from baseline for continuous parameters (analytes) of blood chemistry and hematology tests will be summarized by visit and treatment group using descriptive statistics (mean, median, SD, minimum, maximum, and number of subjects).

Baseline and post-baseline blood chemistry and hematology tests will be classified according to normal ranges as low, normal, and high. Shift of these tests from baseline to the maximum post-baseline values will be presented by treatment group using the number and percentage of subjects at each shift category. If applicable, some laboratory tests have two directions: hypo and hyper, where both directions will be presented in the shift table.

Liver function tests will be summarized by the following:

- Alkaline Phosphatase (ALP)
 - \circ >1.5 × ULN
 - $\circ >2 \times ULN$
 - \circ >3 × ULN
- Alanine Aminotransferase (ALT)
 - $\circ \quad > 3 \times ULN$
 - \circ >5 × ULN
 - \circ >10 × ULN

- Aspartate Aminotransferase (AST)
 - \circ >3 × ULN
 - \circ >5 × ULN
 - $\circ \quad > 10 \times ULN$
- Total Bilirubin (TBL)
 - \circ >1.5 × ULN
 - \circ >2 × ULN
 - \circ >3 × ULN

ULN = upper limit of normal

The risk difference between treatment arms vs placebo, and 95% confidence interval will be calculated.

All laboratory values will be presented in data listings.

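### SAP 5.5.1 reports adverse events only as frequencies and percentages by arm, so the comparison with placebo named in the first safety objective has no effect estimate or measure of precision; a descriptive risk difference with a confidence interval would supply both cheaply

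*Protocol*

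**What the plan says.** **Objective.** Protocol 2.1.3 opens the safety objectives with "To compare the safety and tolerability of liafensine vs placebo in all randomized patients with TRD". SAP 1.1.2 repeats it. Adverse events are the first item in the list of safety endpoints (Protocol 2.2.3, SAP 1.2.2).

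**Protocol analysis.** The synopsis (Safety Analyses) and section 8.3.4 both state: "The incidence and severity of treatment-emergent adverse events (TEAEs) will be summarized by treatment". For categorical safety data they add: "Descriptive summary statistics for categorical data will include frequency and proportion". Safety reporting as a whole is described there as descriptive, and further detail is left to the SAP.

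**SAP analysis of adverse events.** Section 5.5.1 provides: "An overall summary of TEAEs using frequencies and percentages of subjects will be presented based on the following categories". Nine categories follow, including TEAEs leading to withdrawal of study drug. Then: "The following events will be tabulated by SOC and PT". Preferred-term summaries by frequency and listings complete the section. SAP 3.1 defines the displayed groups as placebo, 1 mg, 2 mg and the two doses together.

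**SAP analysis of other safety data.** After the liver-test thresholds, section 5.5.2 states: "The risk difference between treatment arms vs placebo, and 95% confidence interval will be calculated". Section 5.5.3 repeats this for heart-rate changes and for orthostatic drops in blood pressure. For the DESS, section 3.8.6 goes as far as testing: "Treatment comparison will be performed each day from Day 1 to Day 14 using the Cochran-Mantel-Haenszel (CMH) test stratified by region and biomarker status", with a Wilcoxon rank-sum test on the average score.

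**The concern.** The objective is comparative, but the planned adverse-event output stops at one percentage per arm. The reader is left to judge the contrast by eye, with nothing on the page to show how uncertain it is. With about 60 patients per arm, two misreadings are easy: an apparent doubling of a common event on one dose may be chance, and similar percentages may be taken as evidence of no difference when a difference of several points has not been excluded.

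The SAP already considers a risk difference with an interval suitable for some safety data, and it gives no reason for leaving adverse events out. At stake is how clearly the trial answers its own safety objective. No sample size, alpha level, power or efficacy conclusion depends on it.

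**Working it through.** **1. What is planned for each safety output**

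| Output | SAP section | Between-arm statistic |
|---|---|---|
| TEAE overall summary, SOC/PT tables | 5.5.1 | none |
| Liver-test thresholds | 5.5.2 | risk difference, 95% CI |
| Laboratory shift tables | 5.5.2 | none |
| Heart-rate change, orthostatic drop | 5.5.3 | risk difference, 95% CI |
| Maximum blood-pressure categories | 5.5.3 | none |
| C-SSRS | 5.5.4 | none |
| QTcF categories | 5.5.5 | none |
| DESS | 3.8.6 | daily CMH test, Wilcoxon test |

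The gap for TEAEs is confirmed, and adverse events are not alone in it.

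**2. Inputs for the illustration**
- Group sizes: about 180 patients randomized 1:1:1 (Protocol 3.1), so 180/3 = 60 per arm and 120 pooled liafensine against 60 placebo.
- Liafensine rates: headache 14.3% in Study CN162007 and 7.0% in Study CN162006 (Protocol 1.2.1).
- Placebo rate: not given. Those studies used active controls. I assume 2% to 10%.

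The documents state no precision or sample-size figure for safety, so there is none to reproduce. The one sample-size figure, 47 per arm for efficacy, does reproduce: 4.5/(9 × √(1/94 + 1/47)) = 2.80, and 2.80 − 1.96 = 0.84, giving 79.9% power. It has no bearing here.

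**3. Half-width of the missing interval**

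Half-width = 1.96 × √[p₁(1−p₁)/n₁ + p₀(1−p₀)/60]

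For 14.3% on liafensine:
- Pooled, placebo 2%: 1.96 × √(0.143×0.857/120 + 0.02×0.98/60) = 7.2 points.
- Pooled, placebo 10%: 1.96 × √(0.143×0.857/120 + 0.10×0.90/60) = 9.8 points.
- One dose, placebo 2%: 1.96 × √(0.143×0.857/60 + 0.02×0.98/60) = 9.5 points.
- One dose, placebo 10%: 1.96 × √(0.143×0.857/60 + 0.10×0.90/60) = 11.7 points.

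For 7.0% on liafensine, the same formula gives 5.8 to 8.9 points pooled and 7.4 to 10.0 points per dose.

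**4. The method matters at these counts**

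Take 14.3% against an assumed 5%, pooled: the difference is 9.3 points.
- Wald: 9.3 ± 8.3, or 1.0 to 17.6.
- Newcombe: the Wilson limits are 9.1% to 21.7% on liafensine and 1.7% to 13.7% on placebo. The lower limit is 9.3 − √[(14.3−9.1)² + (13.7−5)²] = −0.8. The upper limit is 9.3 + √[(21.7−14.3)² + (5−1.7)²] = 17.4. (Limits are computed from unrounded values.)

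One interval excludes zero and the other does not, with only three placebo events (5% of 60). Sections 5.5.2 and 5.5.3 name no interval method, and Appendix 8 has no code for one.

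**5. Chance doubling for one dose**

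With equal true rates and 60 per arm, exact binomial enumeration gives the probability that the liafensine count is above placebo and at least twice it: 0.143 for a 10% event and 0.261 for a 5% event. Percentages alone do not show this.

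**The case against.** The best defence is that the plan is consistent with itself. The protocol calls safety reporting descriptive and asks only for frequency and proportion. No safety hypothesis, margin or safety-based sample size is stated, and to compare can reasonably mean to set side by side. The tables give n and percentage for placebo, each dose and the pooled doses, so any reader can compute the difference and an interval. A further argument is that the SAP's risk differences go only to selected abnormality thresholds, which looks like a deliberate choice. Finally, intervals for every row would be numerous and unadjusted, and could themselves be mined for signals.

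Most of this stands, and it rules out four stronger readings that a reader might infer:
- *That the objective cannot be answered from the planned tables.* It can be answered informally; what is missing is a reported estimate and its precision.
- *That adverse events are the main safety endpoint and the only one without a comparison.* They are listed first but never called main, and the table above shows others without one.
- *That the protocol and SAP conflict.* They do not; the contrast lies within the SAP, between 5.5.1 and sections 5.5.2, 5.5.3 and 3.8.6.
- *That 14.3% against 7.0% is a drug–placebo contrast.* Both are liafensine rates, from two different studies.

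Nor do the unequal pooled groups mislead by themselves, since percentages allow for group size.

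What the defence does not answer is why the step taken for some safety data should stop short of adverse events. A risk difference with an interval and no p-value is still descriptive, so adding it breaks no statement in the protocol.

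**Conclusion.** The point holds as a low-cost improvement to SAP 5.5.1. A comparative safety objective is served, for adverse events, by per-arm percentages without a between-arm estimate or any statement of precision, while the SAP supplies both for liver-test thresholds, heart-rate change and orthostatic drops.

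Its size is modest. At the planned numbers the unreported uncertainty is about 7 to 10 points either side for pooled liafensine and 9.5 to 12 points for a single dose, for an event at 14.3% on liafensine. These figures are illustrative. They rest on an assumed placebo rate of 2% to 10%, on about 60 treated patients per arm with both DGM4 groups combined, and on the Wald approximation. Displays within DGM4-positive or DGM4-negative patients would be less precise.

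**What to change.** In SAP 5.5.1, add the risk difference against placebo with a 95% confidence interval for 1 mg, 2 mg and pooled liafensine:
- for each row of the overall TEAE summary;
- for each preferred term reported by at least 5% of patients in any arm.

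Name an interval method suited to sparse counts, for example Newcombe or Miettinen–Nurminen, and name the same method in 5.5.2 and 5.5.3. State that the intervals are descriptive, unadjusted for multiplicity and without p-values.

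**Cost.** A few sentences of SAP text and extra table columns, of the type already required for the laboratory and vital-sign tables. No new data and no change to the design.

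**Downside.** Many unadjusted intervals. The nine overall rows alone give 9 × 3 = 27, before severity levels and preferred terms. If no true difference existed and coverage were exactly 95%, 27 × 0.05 = 1.35 of these would be expected to exclude zero. The descriptive label reduces that risk of over-reading but does not remove it.
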